## SCHEMA

Advanced, recurrent or metastatic HNSCC  
Planned to receive immunotherapy (ICI)

ICI      RT      \*May receive up to 3 cycles of RT  
ICI cycle length = every 3 weeks

Blood and saliva collection for correlative analyses  
\*Collected if RT cycle given

## 1.0 Introduction and Background

### 1.1 Introduction

Head and neck cancer is diagnosed in approximately 65,000 patients per year in the United States and causes over 14,000 deaths per year (1). Approximately 90% of all head and neck cancers are squamous cell carcinoma (SCC) of the autodigestive mucosal lining, with other histologies including cutaneous SCC/basal cell carcinoma, melanoma, salivary gland tumors, and others. Generally, 10% of patients have metastatic disease at presentation, 20-30% will develop metastatic disease after definitive treatment, and 40-60% of patients progress within 3-years after curative therapy (2-7). Head and neck cancer is the cause of death in the majority of patients, whether locoregional disease (42.5%) or distant disease (17.9%) (8). Therefore, for those with recurrent or metastatic (R/M) head and neck squamous cell carcinoma (HNSCC), there is strong rationale for the use of second line strategies aimed to: 1) impact disease control on a systemic level and 2) maximize local control at the primary site.

### Role for Immunotherapy in the Management of Head and Neck Cancer

The first-line standard of care (SOC) management for patients with recurrent/metastatic HNSCC includes combination platinum-based chemotherapy plus cetuximab, platinum-based chemotherapy plus pembrolizumab, pembrolizumab alone (for those with combined positive score [CPS]  $\geq 1$ ) (9). Second-line systemic therapy regimens include immune checkpoint inhibitors (ICIs) such as nivolumab or pembrolizumab as single agents after progression on platinum-based therapy (10-14). However, overall response rates (ORR) remain low (Table 1). Additional interventions are direly needed to improve rates of disease response with ICI (with or without chemotherapy), particularly at the primary tumor site, progression of which often leads to significant morbidity and possibly mortality.

**Table 1: Overall Response Rates for Immunotherapy in R/M Head and Neck Squamous Cell Carcinoma**

Study	Overall Response Rate	Agent
KEYNOTE-012	18%	Pembrolizumab
KEYNOTE-040	15%	Pembrolizumab
KEYNOTE-048	17%	Pembrolizumab
	36%	Pembrolizumab + chemotherapy
Checkmate 141	13%	Nivolumab

### Quad-Shot Palliative Radiotherapy for Head and Neck Cancer

Palliative radiotherapy (RT) is a mainstay in the SOC treatment of recurrent or metastatic HNSCC (15). Palliative RT is primarily delivered using external-beam techniques over short courses using larger doses per fraction ( $\geq 3$  Gy per fraction) than conventionally fractionated radiotherapy (1.8-2 Gy per fraction) in an attempt to effect local tumor regression and relief of

Quad-Shot Radiotherapy in Combination with Immune Checkpoint Inhibition for  
 Advanced/Recurrent Head and Neck Cancer  
 Wake Forest Baptist Comprehensive Cancer Center  
 WFBCCC60320

malignancy-related morbidity while limiting acute toxicity. While various fractionations have been reported for this purpose, the quad-shot regimen is a commonly used SOC radiotherapy schedule derived from prior palliative experiences in advanced pelvic malignancy (16, 17). This regimen is comprised of four 3.5 to 3.7-Gy fractions delivered twice daily (BID) over the course of two consecutive days (17-22). This regimen is associated with favorable palliative response rates at the treated site (Table 2). It can also be given concurrently with cytotoxic chemotherapy as reported in two studies detailed in Table 2 (21, 23). Additionally, due to the nature of the hypofractionated regimen and its delivery in split-course cycles, acute toxicity is modest.

Table 2: Quad-Shot Palliative Radiotherapy for Head and Neck Cancer				
Study	Dose/Number of Fractions	Response Rate	Toxicity Rate	Note
Paris et al. (17)	14.8 Gy / 4	CR: 28% PR: 49%	N/A	1-3 cycles delivered with 3-4 weeks between cycles
Corry et al. (19)	14 Gy / 4	CR: 6% PR: 47%	Mucositis G1: 33%; G2: 11%; G3: 0%	1-3 cycles delivered with 3-4 weeks between cycles
Lok et al. (18)	14.8 Gy / 4	Pain response: 66%	Mucositis/dermatitis G3: 5%	1-3 cycles delivered with 3-4 weeks between cycles
Finnegan et al. (20)	14.8 Gy / 4	Pain CR: 39% Pain PR: 22%	Mucositis/dermatitis G2+: 26%/17%	1-3 cycles delivered with 3-4 weeks between cycles
Chen et al. (22)	14.8 Gy / 4	Palliative response: 83%	G3+: 9%	1-3 cycles delivered with 3-4 weeks between cycles.
Carrascosa et al.	14.8 Gy / 4	CR: 14% PR: 71%	Mucositis G3: 14%	1-3 cycles delivered with 3-4 weeks between cycles. Concurrent paclitaxel administered 1 hour prior to the first fraction of each cycle.
Gamez et al.	14.8 Gy / 4	CR: 24% PR: 62%	Mucositis/xerostomia G2: 35%	1-3 cycles delivered with 3-4 weeks between cycles. Concurrent carboplatin or cetuximab administered 1 hour prior to the first fraction of each cycle.

However, the quad-shot regimen is not sufficient to provide a definitive dose for durable disease control. The equivalent dose in 2-Gy fractions (EQD2) (assuming  $\alpha/\beta=10$  [tumor]) for a single cycle is 16.9 Gy, 33.8 Gy for 2 cycles, and 50.7 Gy for 3 cycles. In prior studies, approximately

Quad-Shot Radiotherapy in Combination with Immune Checkpoint Inhibition for  
Advanced/Recurrent Head and Neck Cancer  
Wake Forest Baptist Comprehensive Cancer Center  
WFBCCC60320

64% of patients are eligible to receive more than one quad-shot cycle, and palliative response rates correlate with number of cycles delivered: 55% for 1 cycle, 44% for 2 cycles, 88% for 3 cycles (correlation coefficient 0.29, p=0.012) (18). Despite its fairly favorable rates of achieving palliation at the treated site, this palliative (rather than curative) regimen is insufficient for long-term disease control at the target site. Duration of control (DOC) has been reported in a phase II study also included in Table 2 (19). Median DOC was 5.7 months at the primary and 5.2 months at nodal sites for those with CR/PR and 1.8 months at the primary and 9.5 months at nodal sites for those with stable disease. Considering that advancements in systemic therapy using ICI have prolonged median survival for this patient cohort to 12 months or more, most patients will experience local and/or regional progression that may result in significant morbidity or even mortality. Therefore, there is strong rationale for combination therapy with PRT + immunotherapy for both patients with recurrent, advanced, incurable local disease or metastatic disease with an untreated primary.

Rationale for the Combination of Quad-Shot Radiotherapy and Immunotherapy

The mechanism of conventionally-fractionated RT (1.8-2 Gy per fraction) is to induce clonogenic cell death in target cells by generating irreparable DNA damage. This is achieved indirectly through the generation of reactive oxygen species or directly by ionizing the DNA itself. For palliation, more hypofractionated regimens such as quad-shot are often utilized. It is now apparent in preclinical data that hypofractionated radiotherapy impacts many components of the tumor microenvironment including CD8 T-cells, dendritic cells/antigen-presenting cells, cytokine expression, MHC expression, regulatory T-cells, interferon-gamma expression, MHC expression, and others (24).

Immune checkpoint inhibition has been studied in combination with radiotherapy in preclinical models with the goal of increasing efficacy through RT-mediated increase in tumor immunogenicity (25). The combination of hypofractionated radiotherapy with anti-CTLA-4 antibodies or with PD-1 pathway blockade seems to enhance the effects of RT on tumor kill (26-28). RT has been shown to induce a significant increase in major histocompatibility complex (MHC) molecular expression in tumor cell lines and may re-sensitize tumors resistant to anti-PD-1 therapy causing regression in the target primary and non-irradiated (non-target) tumors (29). Additionally, tumor cells and other cells in the tumor microenvironment upregulate PD-L1 expression after RT, and the combination of ICI and RT may increase tumor kill by enhancing the efficacy of established T-cell mediated tumor immunity (30).

It appears that RT regimens using hypofractionated radiotherapy (a few fractions of doses higher than 2 Gy per fraction) improve tumor control when combined with ICI. Because T cells are sensitive to low doses of radiation, it is thought that conventionally fractionated radiotherapy over the course of several weeks may deplete the tumor immune response by local depletion of tumor-specific immune cells (31). In a mouse model, synergistic effects are increased when RT is given in the days prior to ICI or on the same day (32). Other preclinical evidence points to a benefit with ICI is administered prior to radiotherapy (30, 33). No clear clinical evidence exists to support the timing of ICI combined with RT, and currently, administration of ICI and radiotherapy on the same day is avoided given concerns for increased RT and immune-mediated adverse effects. It is worth noting that this practice is borne from an abundance of caution among oncologists and that it is not clear there is increased toxicity with concurrent administration of ICI

Quad-Shot Radiotherapy in Combination with Immune Checkpoint Inhibition for  
Advanced/Recurrent Head and Neck Cancer  
Wake Forest Baptist Comprehensive Cancer Center  
WFBCCC60320

and RT—recent and ongoing clinical trials are testing the efficacy of conventionally fractionated concurrent with ICI (RTOG 3504: NCT02764593, HN-005: NCT03952585).

Current standards of care for patients receiving palliative RT while on ICI or chemo-ICI is to deliver the RT between administrations of systemic therapy. The half-life of pembrolizumab is on the order of 14-27 days and reaches steady-state after approximately 6 every-3-weekly cycles (34). We hypothesize that this combination and the timing detailed in the schema will provide sufficient PD-L1 blockade at the time of quad-shot radiotherapy. It has been suggested that RT doses in the range of 14-24 Gy in 2-3 fractions with concurrent ICI may be the most appropriate to utilize in further study (25). It is important to note that the quad-shot regimen falls close to this optimal range (14.4 Gy in 4 fractions). Additionally, prior reports indicate this dosage may be able to produce an abscopal effect in patients treated with ICI in metastatic head and neck squamous cell carcinoma (35). In all, this regimen is well-established in the literature to be safe and effective for head and neck cancer, can be delivered safely as RT alone or in combination with cytotoxic chemotherapy.

The combination of ICI with radiotherapy has been found to be safe for patients with intermediate- or high-risk squamous cell carcinoma of the head and neck in preliminary studies (36, 37). Early-phase studies have also demonstrated safety with hypofractionated (3 Gy per fraction) regimens and stereotactic body radiotherapy (SBRT), a technique which employs larger fraction sizes (8 Gy per fraction) (38, 39). The data presented herein provide strong rationale for further clinical study into the efficacy of quad-shot radiotherapy combined with ICI.

## 2.0 Objectives

This pilot study aims to assess the efficacy and tolerability of short-course quad-shot radiotherapy in combination with immunotherapy. Both of these standard-of-care treatments have the potential to act synergistically to improve response rates to systemic therapy. This study will study the effects of combining these standard treatments in a novel sequence. For the purposes of this study, the term immunotherapy will be used to specifically reference the use of the immune checkpoint inhibitor pembrolizumab.

The hypothesis is that the delivery of palliative quad-shot radiotherapy in combination with immunotherapy is feasible and improves the response rates at the treated site.

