### 2.1 Primary Objective(s)

2.1.1 Measure the overall response rate for immunotherapy given with quad-shot radiotherapy

### 2.2 Secondary Objective(s)

2.2.1 Measure the response rate at the target lesion.

Quad-Shot Radiotherapy in Combination with Immune Checkpoint Inhibition for  
Advanced/Recurrent Head and Neck Cancer  
Wake Forest Baptist Comprehensive Cancer Center  
WFBCCC60320

- 2.2.2 Measure the response rate at non-target sites *in patients with non-target sites.*
- 2.2.3 Evaluate the durability of response at the target lesion.
- 2.2.4 Evaluate progression-free survival.
- 2.2.5 Evaluate overall survival.
- 2.2.6 Assess the tolerability of the combination of quad-shot radiotherapy with immunotherapy in order to assess the feasibility of this treatment regimen.

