### 11.2 Analysis of Secondary Objective

There are 6 secondary outcomes of interest for this pilot study. These are 1) response rate for the target lesion; 2) response rate for non-target lesions 3) duration of response for the target lesion 4) progression free survival (PFS) 5) overall survival (OS) and tolerability assessed using PRO-CTCAE. We now describe our analytic approach for each measure.

For the response rate measures we will estimate the percent of responders (PR or CR) and the corresponding 95% Clopper Pearson exact confidence intervals. For the duration of response, among responders we will estimate both the mean and median duration and the corresponding 95% confidence intervals for the mean and inter-quartile range for the median. For time to event measures (PFS and OS) we will estimate Kaplan Meier survival curves and estimate the median time to event times as well as the percent PFS and OS at 6 months and 1 year post treatment. For tolerability, we will estimate the percent of patients with different AEs assessed using the PRO-CTCAE and corresponding 95% Clopper Pearson exact confidence intervals.

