### 11.3 Power and Sample Size

Since this is a pilot study there will be no formal hypothesis tests performed. With a sample size of 15 evaluable patients (patients must be evaluable for objective response as described in Section 7.1.1), the maximum width of a 95% Clopper Pearson exact confidence interval is 0.52 (since the interval may not be symmetric this corresponds to approximately +/- 0.26 (if the response rate is as high as 7/15). If the response rate is lower than this then the width of the confidence interval will be less. With this sample size we will be able to determine whether the response rate in this treatment is high enough to warrant future examination. Based on preliminary data presented in Table 1 the response rates from previous studies is between 13 and 36% thus we would anticipate that the response rate in this study will need to be at least this high to warrant future studies.

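### The treated-site hypothesis names no comparator, and the plan's only benchmark (13-36%, immunotherapy listed without radiotherapy) could be cleared by the local effect of radiotherapy alone

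*Combined protocol and SAP*

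**What the plan says.** Section 2.0 gives one hypothesis: "delivery of palliative quad-shot radiotherapy in combination with immunotherapy is feasible and improves the response rates at the treated site". It does not say what the rate improves on.

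The primary objective (2.1.1) is different: "Measure the overall response rate for immunotherapy given with quad-shot radiotherapy". Response at the treated site is secondary (2.2.1): "Measure the response rate at the target lesion". Section 11.2 analyses it by estimation: "For the response rate measures we will estimate the percent of responders (PR or CR) and the corresponding 95% Clopper Pearson exact confidence intervals". No reference value is attached.

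Section 11.3 disclaims testing: "Since this is a pilot study there will be no formal hypothesis tests performed". It then takes a range of 13 to 36% from Table 1 and adds: "we would anticipate that the response rate in this study will need to be at least this high to warrant future studies". Table 1 lists overall response rates for pembrolizumab, pembrolizumab plus chemotherapy, and nivolumab. Radiotherapy appears in none of its rows.

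Two other parts of the protocol bear on this:

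- Section 7.1.1 defines the lesions chosen for quad-shot, at most two, as the target lesions. All other recorded lesions are non-target and need not be measured.
- Table 2 in the background section reports response to quad-shot, and the text introducing it refers to the treated site. Section 11 does not use it.

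**The concern.** A claim of improvement needs something to improve on. At an irradiated lesion the first alternative explanation for shrinkage is the radiotherapy itself. The protocol holds figures for that effect in Table 2, but the only range brought into the statistical section comes from systemic therapy.

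The issue also reaches the primary endpoint. Because only irradiated lesions are measured as target lesions, the overall response rate depends heavily on what radiotherapy does locally. That rate is then set beside rates from studies listed without radiotherapy. A result above 13-36% could be taken as a sign that the two treatments work together when it reflects local radiotherapy alone. The stated purpose is to judge whether the regimen deserves further study, so this affects what the 15 patients can be said to show.

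**Working it through.** **The plan's own figure.** The inputs are "With a sample size of 15 evaluable patients" and the statement that "the maximum width of a 95% Clopper Pearson exact confidence interval is 0.52". The Clopper-Pearson limits for x responses in n are the 0.025 quantile of Beta(x, n-x+1) and the 0.975 quantile of Beta(x+1, n-x). For 7/15 they are 0.213 and 0.734, a width of 0.5215. No other count gives a wider interval (8/15 ties), so the 0.52 reproduces.

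**Radiotherapy-only rates (Table 2).** Two rows give tumour CR and PR for quad-shot without systemic therapy:

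- Phase II study (reference 19): 6% + 47% = 53%.
- Phase I-II study (reference 17): 28% + 49% = 77%.

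The other radiotherapy-only rows report pain or palliative response. The two rows with concurrent systemic therapy give 14% + 71% = 85% and 24% + 62% = 86%.

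**From target lesion to overall response (7.1.3).** A target PR with non-target disease that has not progressed and no new lesion is an overall PR. A target CR with persisting non-target disease is also an overall PR. Every overall CR or PR requires a target CR or PR. Overall response therefore cannot exceed target-lesion response, and equals it unless there is non-target progression or a new lesion.

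**Chance of clearing the benchmark if pembrolizumab adds nothing at the treated site.** Since 5/15 = 33% and 6/15 = 40%, an observed rate above 36% needs 6 or more. P(X ≥ 6) is the sum over k = 6 to 15 of C(15,k) p^k (1-p)^(15-k).

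| Event (n = 15) | True rate 53% | True rate 77% |
|---|---|---|
| ≥ 2/15 (13.3%, above 13%) | 0.9998 | > 0.999 |
| ≥ 6/15 (40%, above 36%) | 0.898 | 0.9996 |
| ≥ 7/15 (lower 95% limit above 18%) | 0.774 | 0.998 |
| ≥ 10/15 (lower 95% limit above 36%) | 0.213 | 0.892 |

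These are exact for target-lesion response and upper bounds for overall response.

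**How far below the bound?** This depends on the share of target-lesion responders who do not count overall because of progression elsewhere. The documents give no figure, so the share is an assumption:

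- From 77% down to 53% takes a share of 1 - 53/77 = 31%, and P(≥ 6/15) is still 0.90.
- From 53% down to 36% takes a share of 1 - 36/53 = 32%, and P(≥ 6/15) is 0.47.
- For comparison, at a true rate of 18%, the highest single-agent rate in Table 1, P(≥ 6/15) is 0.039.

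**What 15 patients can say against Table 2.** An observed 8/15 (53%) has limits 0.266 to 0.787, which contain both 53% and 77%. The lower limit first exceeds 53% at 13/15 (0.595; 12/15 gives 0.519) and first exceeds 77% at 15/15 (0.782).

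**The case against.** The strongest reply is that the comparator may be immunotherapy. Section 2.0 also speaks of raising response to systemic therapy, and the background asks for additions that raise response to checkpoint inhibitors, especially at the primary site. On that reading radiotherapy is the added component and its local effect is part of the gain sought. This stands as a legitimate reading. It is not the only one the text allows, which is why the comparator should be named.

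Second, a reader might infer that the plan judges treated-site response against 13-36% and would call a radiotherapy effect a success. The documents do not support that. Table 1 holds overall response rates, matching the primary endpoint. Section 11.2 only estimates target-lesion response, and Section 11.3 words the range as a necessary condition, not as proof of improvement. What remains is that the overall rate set beside that range is itself driven by the irradiated lesions.

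Third, 53-77% is a weak reference. The two reports date from 1993 and 2005 and RECIST 1.1 from 2009, so they did not use it. The 53% row used 14 Gy per cycle, against 14.8 Gy here. Table 2 cycles were 3-4 weeks apart. Here a second cycle comes at least three immunotherapy cycles after the first (3 × 3 = 9 weeks), only one is mandated, and the first response evaluation falls before any second one. The background also reports that palliative response correlates with the number of cycles. This stands: the range is context, not a null value.

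Fourth, this is a declared single-arm pilot without tests, and it already plans non-target response and target-lesion durability. That is true and lowers the stakes, but neither tells a reader how to interpret a rate above 36%.

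**Conclusion.** The point holds in a limited form. The hypothesis lacks a comparator, and the plan's only benchmark does not separate a combined effect from a local radiotherapy effect. If the radiotherapy-only rate at the treated site is 53%, the top of the benchmark is passed with probability up to 0.90. At 77% the bound is above 0.99. Clearing 13-36% is therefore not evidence that the combination adds to radiotherapy.

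This rests on three assumptions: that Table 2 rates roughly indicate what quad-shot does under this protocol's criteria and schedule; that patients respond independently; and, for overall response, that few target-lesion responders progress elsewhere before their response is recorded.

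Two stronger conclusions are not supported. One is that the plan would declare success on a radiotherapy effect; it sets no success rule for the treated site. The other is that improvement should be claimed when the lower limit exceeds 53%, that is, at 13/15. That would put a de facto test into an estimation-only pilot. If radiotherapy alone gave 77%, it would be met 29% of the time with no contribution from pembrolizumab.

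**What to change.** - **Sections 11.2 and 11.3.** Report target-lesion response with its exact interval beside the Table 2 radiotherapy-only rates (53% and 77%) as context. Note the differences in response criteria, dose and cycle spacing. State that exceeding 13-36% is not evidence of benefit over radiotherapy alone.
- **Section 11.1.** Report overall response separately for patients with and without unirradiated disease at baseline, alongside the planned non-target response. In patients without such disease, overall response is the treated-site response unless a new lesion appears.
- **Section 2.0.** Name the comparator for the hypothesised improvement, or reword the sentence as estimation only.
- Do not add a 13/15 or similar success rule.

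The cost is a few sentences and no extra patients or assessments. The downside is that splitting 15 patients gives small groups with wide intervals, and the claim available from the study becomes more modest.
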